## Study Synopsis

Full Title	Online guided self-help intervention for sexual distress following sexual assault: A single case experimental study
Short Title	Guided self-help following sexual assault - SCED
Protocol version number and date	V2 250722
Study duration	10 months
Study design	Single Case Experimental Design
Sponsor	Royal Holloway, University of London
Chief Investigator	[name]
IRAS Project ID	313482
Primary objective	To test the acceptability and feasibility of an online guided self-help intervention by female survivors of sexual assault who experience sexual distress
Secondary objective	To gain an initial indicator on the effectiveness of the intervention
Number of subject	6
Main inclusion criteria	Cis-female over the age of 18 with an experience of sexual assault that occurred over 12 months ago
Statistical methodology and analysis	Descriptive statistics, visual analysis, reliable change index.

## 1. Background & Aims of the project

### **1.1 Need for research in this area**

Sexual assault (SA) is associated with enduring negative impacts, including interpersonal, psychological and physical difficulties (Maniglio, 2009; Chen et al., 2010). SA survivors develop a different relationship with sex (O'Callaghan et al., 2018) and report less interest in sex, reduced desire, fear of sex, arousal dysfunction and painful sex (Norris & Feldman-Summers, 1981; Weaver, 2009). They also experience high levels of shame, self-blame and decreased self-compassion and attachment-based difficulties (Hamrick & Owen, 2019).

Despite the prevalence of these difficulties, there is limited research identifying treatment. Systematic reviews investigating the effectiveness of psychological interventions in SA survivors do not mention sexual distress, suggesting that interventions are limited or do not consider sexual distress (Regehr et al., 2013; Parcesepe et al., 2015). Instead, they target generic distress related to trauma. Evidence from a meta-analysis suggests that psychological treatments for post-traumatic stress disorder following SA had no effect on sexual problems (O'Driscoll & Flanagan, 2015). On the other hand, traditional psychosexual therapy that aim to alleviate sexual distress does not consider the experience of SA trauma symptoms and how they may interact with standard psychosexual approaches (Althof et al., 2005). Meston and colleagues (2013) found that standard psychosexual therapy developed to alleviate sexual difficulties had inconsistent results among women with a history of SA, suggesting precedence for developing specific psychosexual intervention for SA survivors. Few studies explored specific interventions for sexual distress experienced by SA survivors; however, most of these studies do not adopt a formal model or follow a standard protocol (Gerwitz-Meydan, 2020).

This study proposes an online four-session guided self-help psychoeducational program for survivors of SA. Online guided-self-help is the chosen modality as it widens access to treatment in a population who may experience shame and stigma regarding help-seeking (Levin et al., 2018). Previous studies, such as a pilot RCT found online guided self-help effective in improving sexual functioning in women with vaginismus (Zarski et al., 2017). A treatment protocol for Internet-based guided self-help has already been developed for sexual pain but not for sexual distress after SA (Zarski et al., 2018). This intervention aims to normalise and build women's confidence on getting back to sex after experiencing SA. The objective is to reduce shame, self-criticism, sexual distress and improve sexual well-being. By exploring an individual's difficulties through a normalising framework, the intervention aims to increase their awareness of their difficulties and build confidence, skill and motivation to alleviate sexual distress. As this is a novel intervention, the study adopts a single-case experimental design (Morley, 2017). It aims to test the acceptability and feasibility and potential effectiveness of the intervention.

To our knowledge, no research projects have developed guided self-help materials for female survivors of sexual abuse targeting sexual distress. The project has taken guidance from experts by experience to develop materials collaboratively. Clinical psychologists from Bart's NHS Trust Sexual Wellbeing Service, where similar materials have been used in a group setting have also provided feedback.

## **1.2 Aims**

- To investigate the feasibility and acceptability of a 4-session guided self-help psychosexual intervention for survivors of sexual abuse
- Initial indicator of effectiveness in reducing sexual distress

- Improving sexual satisfaction— specifically confidence in practicing strategies that will improve their relationship and experience of sex

### **1.3 Study objectives**

#### *Primary objectives*

- a. The objective of the study is to investigate the feasibility and acceptability of a 4-session guided self-help intervention for female survivors of sexual assault to gather an initial indicator of effectiveness in reducing sexual distress.
- b. Is the intervention viewed as acceptable by female survivors of sexual assault? We will be defining ‘acceptability’ as how willing participants are to use the materials and its content (Bowen et al., 2009).

#### *Secondary objectives*

The secondary outcomes are whether the study suggest the intervention is effective. Is there an initial indicator that the intervention effective? Effectiveness is measured by reduction in the measure of sexual distress and improvement of sexual satisfaction – specifically confidence and motivation in practicing strategies that will improve their experience of sex.

## **2. Methods**

### **2.1 Study design**

The study adopts a single-case experimental design (SCED). This study design is helpful in testing the novelty and feasibility of an intervention.

Potential participants will be invited to follow a link to a Qualtrics survey. The Qualtrics survey provides detailed information about the study. Participants will undergo screening for eligibility and risk via Qualtrics. Should individuals wish to participate and are eligible, they can give informed consent by reading a set of statements on Qualtrics relating to the study

information. Eligible participants will fill in questionnaires such as the FSDI, FSFI, SCSS-S, at this point. Participants will undergo a baseline period known as phase A, varying between 5- 14 days where they will fill in visual analogue scales daily. The number of days participants will be in baseline will be randomly allocated by a randomiser. There are 6 visual analogue scales measuring shame, guilt, self-criticism, self-compassion, normalising and motivation. After phase A, participants will undergo phase B, which is a 4-week intervention period where participants go through 1 module of the guided-self-help materials each week and complete the same visual analogue scales from baseline every day. After phase B, participants will be invited for a follow-up appointment one month after the intervention to fill in the FSDS, FSFI, client satisfaction questionnaire (Larsen et al., 1979) and feedback form developed with experts by experience.

## **2.2 Recruitment and participant screening**

The study will be advertised through Barts NHS Trust Sexual Wellbeing Service with information put on leaflets circulated within the clinic. Clinicians may also provide an information sheet to clients with a weblink the study details and screening questionnaire.

Additional recruitment will be done on My Body Back, an organisation who works with women with experience of sexual assault, in London and Glasgow. My Body Back will advertise the study on its website and at its events, providing a web link to the study details and initial screening questionnaire. The intervention will be offered whilst women are on the waiting list. They will not lose their place on the waiting list if they take part.

General social media advertising will also be done through different charities and communities who work with female survivors of sexual assault. Potential participants will be encouraged to take some time to think about whether or not they would like to participate. Individuals will be

informed that participation is on a voluntary basis and consent can be withdrawn at any time. They will also not lose their place on the waiting list for services. Statistical power analyses have been underdeveloped for SCED (Arntz et al., 2013). For a SCED, only 1 participant is required for analysis but, Lanovaz & Rapp (2015) suggest a '3 point guideline' as the minimum requirement for control of study design. Having more than 3 participants will also improve the generalization of findings (Kratochwill et al., 2013). Considering this and to account for attrition, we aim to recruit 20 participants with a minimum sample size of 6 participants.

Should individuals wish to participate they will be invited to follow a link to a Qualtrics survey to initial screening questions to check for eligibility. Prior to completing the screening questionnaire participants will be provided the following text 'Thank you for being interested in this study. The next step is to complete a screening questionnaire. This questionnaire aims to determine if this study would be appropriate for you. The questionnaire does not ask you direct questions about your experience of sexual assault; however, it could potentially elicit difficult emotions. Please keep this in mind if you decide to proceed with the questionnaire as your wellbeing is a priority. There are no consequences if you decide to opt out of participating in this study. At the end of the questionnaire, we have included the chief investigator's email along with signposting information about services you can contact if you require additional support. Thank you for your time.' These questions will confirm if participants are experiencing difficulties with sex, have been sexually assaulted over 12 months ago, if they are currently receiving other forms of psychological intervention and have access to a smart phone or computer to access materials. The Patient Health Questionnaire 2-item (PHQ-2) and Generalised Anxiety Disorder 2-item (GAD-2) are incorporated in the screening questionnaire not to screen for depression and/or anxiety but provide an indication of participant demographic. There will also be a risk screen based on the PHQ-9 "Over the past two weeks,

how often have you been bothered by thoughts that you would be better off dead or of hurting yourself in some way?" - Not at all, Several days, More than half of the days, Nearly every day and a question about support from family and friends. Those who rate themselves as experiencing thoughts of death or self-harm and do not indicate that they have social support or psychological support will not be eligible to participate (see section. Those ineligible to participate will be redirected to a debrief page, 'debrief page for Qualtrics', which will include an explanation of why this is the case and signposting to relevant resources. They will also be provided with the chief investigators email or given the option to leave their telephone number for the chief investigator to call them and discuss why they were not appropriate for the study. Eligible participants will provide informed consent by reading statements relating to the study information and writing their initials if they consent to each statement. This includes confirming they have read the information, understanding participation is voluntary and being able to withdraw from the research at any time. Participants are asked to provide their GP details as part of informed consent. Participants will be informed that their GP will not be notified about their involvement in the study or provided any information contributed whilst participating. We will only contact their GP if there are identified risks. These risks include increased self-harm behaviour, increased suicidal risk or significant deterioration of mental health. Under these circumstances, confidentiality may be breached and, the chief investigator may contact the participants GP. As there is little to no professional contact as part of the study design, the chief investigator will only be made aware of increased risk if the participant raises it to the chief investigator by email.

Eligible participants who provide informed consent will have a screening call with the lead investigator, [name] to verify risk, confirm consent and answer any additional questions about the study. As the intervention is online, we hope that having a call at the

beginning will increase engagement through the study. After the screening call, participants will be asked to fill in a participant demographic sheet and provide their name, age, ethnicity, email address (for contact), region in the UK they live in, employment status and if they are currently or have previously accessed psychological therapy and what type of therapy they received. In addition, participants will complete the Female Sexual Distress scale – Revised (FSDS-R; Derogatis et al., 2002), Female Sexual Function Index (FSFI; Rosen et al., 2000) and State Self Compassion Questionnaire (SSCS-S; Neff et al., 2021).

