### *2.2.2 Exclusion criteria*

Participants will be excluded if they are experiencing severe acute mental health difficulties, sexual assault occurring within the last 12 months or currently experiencing more than fleeting suicidal thoughts or engaging in severe self-harming (individuals who have been sexually assaulted are likely to experience suicidal thoughts or self-harm behaviours, individuals with fleeting suicidal thoughts or superficial self-harm with strong protective factors may be

included however, since there is no contact with mental health professionals during the intervention unless participants reach out for triage, it is difficult to assess risk and participants have to be excluded if they do not have social support systems or are currently accessing psychological support).

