### **3.3 Statistical analysis of data**

Descriptive statistics will be completed for demographic information. Visual analysis will be performed for daily VAS ratings to evaluate the reliability of treatment effects between the baseline and treatment phases. To investigate if there is pre-and post-difference between scores a reliable change index (RCI) will be calculated for each measure using Jacobson & Traux (1991) to test if changes are statistically significant. Tau-U test will be used on outcomes to analyse non-overlap of intervention scores. Guidance and procedures will be followed from What Works Clearing House (Kratochwill et al., 2010).

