Participants will be assessed on their risk to self during screening and receive a follow-up screening call from the head investigator. Participants who disclose high risk who are not accessing mental health services will be excluded from participating to prevent further distress that may be triggered during the intervention. Participants will be made aware that the researcher cannot provide advice or medical treatment and that they should contact their GP as a first step if they have concerns regarding their mental or physical health. Participants will be

able to provide details of their GP who can be informed that they are taking part in the study, however this is not compulsory.

Overall, the potential benefits of this study are thought to outweigh the risk. The intervention content is based on compassion-focused therapy and content that is already used by Barts NHS trust Sexual Wellbeing Service to improve sexual wellbeing. Participants can access the materials while waiting to be seen by these services, both of which have a long wait time.

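### Some participants are on therapy waiting lists, but therapy started after entry is not recorded, so a reliable change it causes could be credited to the intervention

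*Combined protocol and SAP*

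**What the plan says.** All references are to the combined protocol and SAP.

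- **Recruitment (2.2).** For women waiting for a service, "The intervention will be offered whilst women are on the waiting list", and taking part does not cost them their place. Section 3.4 repeats this: "Participants can access the materials while waiting to be seen by these services, both of which have a long wait time". There is also a route that need not involve a list: "General social media advertising will also be done through different charities and communities".
- **Recording of other therapy (2.2).** The screening questions ask "if they are currently receiving other forms of psychological intervention". The demographic sheet, completed after the screening call, asks "if they are currently or have previously accessed psychological therapy and what type of therapy they received". Both are completed once, at entry.
- **Exclusion (2.2.2).** The text says "participants have to be excluded if they do not have social support systems or are currently accessing psychological support". The wording is ambiguous, but on any reading it concerns status at entry.
- **Follow-up (2.1, 2.3.7, 3).** Across these sections the instruments are the sexual distress and sexual function scales, the self-compassion scale, the satisfaction questionnaire and a feedback form with open questions about the intervention. No item on other treatment is listed.
- **Analysis (3.3).** For pre-post differences, "a reliable change index (RCI) will be calculated for each measure". Sections 2.3.3 to 2.3.5 place those measures at recruitment and at the 1-month follow-up. Visual analysis is applied to the daily visual analogue scale (VAS) ratings in phases A and B, and Tau-U to outcomes.
- **Use of the result (1.3).** Effectiveness, the secondary objective, is judged by a fall in sexual distress and better sexual satisfaction.

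**The concern.** The RCI asks whether a person's score moved by more than measurement error would explain. It does not say why. In this design the pre-post comparison has no comparator, and one recruitment route selects women who are due to start treatment for the same problem. At one of the recruiting services that treatment may overlap with the intervention: section 3.4 describes the material as drawing on "content that is already used by Barts NHS trust Sexual Wellbeing Service to improve sexual wellbeing".

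A woman who reaches the top of the list during the study and improves would be counted as a reliable improver on the self-help materials. Section 3.3 has no rule, adjustment or sensitivity analysis for this, and the planned data would not show which participants it applied to. With a minimum of 6 participants, one misattributed case moves the proportion with reliable improvement by 1/6, about 17 percentage points.

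**Working it through.** The plan states no figure on this point, so there is none to reproduce. The check has four steps.

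**1. Window of exposure.** Inputs from section 2.1: phase A 5 to 14 days, phase B 4 weeks (28 days), follow-up one month later (28 to 31 days).

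- Shortest: 5 + 28 + 28 = 61 days.
- Longest: 14 + 28 + 31 = 73 days.
- Share falling after phase B: from 28/70 = 40% (14-day baseline, 28-day month) to 31/64 = 48% (5-day baseline, 31-day month).

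No daily ratings are scheduled in that last part.

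**2. Chance of a therapy start.** The documents give no waiting time, so this is an assumption: every participant is on a list, and the remaining wait is uniform over W days. Then p = window/W, and the chance of at least one start among 6 is 1 − (1 − p)^6.

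| Assumed W | p | Expected of 6 | Expected of 20 | At least one of 6 |
|---|---|---|---|---|
| 12 months (365 days) | 61/365 to 73/365 = 17-20% | 1.0-1.2 | 3.3-4.0 | 67-74% |
| 24 months (730 days) | 61/730 to 73/730 = 8-10% | 0.5-0.6 | 1.7-2.0 | 41-47% |

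These are chances of starting therapy, not of a false reliable change.

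**3. Chance that a start leads to reliable change.** The Jacobson-Truax threshold in SD units is 1.96 × √2 × √(1 − r). The only numerical reliability in the plan is alpha = .86 for the self-compassion scale (2.3.5), used here for illustration. This gives S_diff = √2 × √0.14 = 0.529 and a threshold of 1.96 × 0.529 = 1.04 SD. With no intervention effect, P(reliable improvement) = Φ(d/0.529 − 1.96), where d is an assumed shift due to therapy:

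- d = 0: 2.5%
- d = 0.5 SD: 16%
- d = 0.8 SD: 33%
- d = 1.0 SD: 47%

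**4. Steps 2 and 3 combined.** With q the probability from step 3, the chance that at least one of 6 both starts therapy and shows a reliable improvement is 1 − (1 − pq)^6, for d from 0.5 to 1.0 SD:

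- 12-month assumption: pq = 0.026 to 0.094, giving 15-45%.
- 24-month assumption: pq = 0.013 to 0.047, giving 8-25%.

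Both ranges lean high. They put all 6 participants on a list, and they give each therapy start its full effect by follow-up even if it came only days before. If 3 of 6 were on a list, the exponent becomes 3 and the ranges fall to 8-26% and 4-14%.

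**The case against.** Much of the case on the other side stands.

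- **Waits are described as long (3.4).** This makes a start within 9 to 10 weeks less likely. But no figure is given, women can enrol part-way through a wait, and therapy can begin elsewhere.
- **The single-case design offers some protection.** Randomised baseline lengths and daily ratings could show when a change occurred in phases A and B. Section 3 also says the questionnaires are completed weekly in those phases, which disagrees with sections 2.3.3 to 2.3.5 and needs reconciling. Such data could date a change but not explain it, and neither schedule covers the weeks between phase B and follow-up.
- **Effectiveness is secondary.** Feasibility and acceptability are primary, and only an initial indicator of effect is sought. This limits the weight of the point.

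Four stronger readings are tempting but not supported:

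- *That the information would be lost for good.* Section 5.1 keeps a key linking names to IDs until contact is no longer needed, and email addresses are held, so participants could be asked later. What is missing is planned, systematic recording.
- *That use of the 1:1 support session is equally unrecorded.* Under sections 3.4 and 4 requests go through the investigator, and the pause rule in 3.6 depends on counting them over time.
- *That the waiting services deliver the same content.* Section 1.1 says similar materials were used in a group at the Barts service. Nothing of the kind is said of the other recruiting organisation.
- *That a therapy start means a false reliable improvement.* Step 3 of the working shows that, for assumed shifts of 0.5 to 1.0 SD, fewer than half would cross the threshold.

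**Conclusion.** The gap is real and minor. Followed as written, the plan could count a change brought about by newly started therapy as a reliable improvement on the intervention, and it collects nothing systematically that would reveal this. The RCI at follow-up is the result mainly affected. The VAS analyses are touched only by therapy begun before phase B ends.

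The size cannot be fixed from the documents. The 8-20% chance of a start in the window rests on assumed uniform remaining waits of 12 to 24 months and on every participant being on a list. The 8-45% chance of at least one such reliable improvement among 6 further assumes a therapy effect of 0.5 to 1.0 SD, realised in full by follow-up, and borrows one scale's reliability. These figures show that the problem could matter in a series this small. They do not estimate how often it will occur.

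**What to change.** 1. Add one item to the 1-month follow-up survey: any other psychological therapy started since enrolment, with type and start date.
2. In section 3.3, state that RCI results will be reported for all participants and again without those who started other therapy. Where the start date falls in phase A or B, mark it on that participant's VAS graph. A start in the follow-up month cannot be shown there, because the ratings have ended, so it should be listed beside the RCI result.
3. Take use of the 1:1 session from the investigator's existing contact record. No extra question is needed.

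The cost is one survey item and a sentence or two of analysis text. Treatment, eligibility and visit schedule are unchanged. The downside is that the result without those participants rests on fewer people, which matters with a minimum of 6, so it should be read as a sensitivity check.

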### *2.2.1 Inclusion criteria*

- Cis female experiencing sexual distress with a history of sexual trauma
- Willingness to complete guided self help
- Aged 18 and above
- Ability to read English to provide consent and meaningfully engage with the self-help materials
- Ability to access online guided self-help material through a computer or phone
- Not currently experiencing severe acute mental health problems
- Not currently suicidal or self-harming

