#### *2.3.3 Female Sexual Distress scale – Revised (FSDS-R; Derogatis et al., 2002)*

The FSDS-R is used to assess distress related to sex in women (Derogatis et al., 2002). This 13-item self-report questionnaire is scored has four points, (0: never; 1: rarely; 2: occasionally; 3: frequently). In multiple studies involving more than 500 women, the FSDS-R has shown

high internal consistency (Dergostis et al., 2008) for women with and without sexual difficulties. A validation study demonstrate that the measure has discriminant and content validity (Dergostis et al., 2008). The FSDS-R is completed upon recruitment and at the 1 month follow up.

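### Entry requires sexual distress, but no screening step as described tests for it, so a woman whose baseline FSDS-R is too low to fall reliably could enrol

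*Combined protocol and SAP*

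**What the plan says.** All references are to the combined protocol and SAP unless stated.

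- **Criterion.** Section 2.2.1 lists "Cis female experiencing sexual distress with a history of sexual trauma". It names no instrument, item or cut-off for distress. The synopsis summarises the main criterion as "Cis-female over the age of 18 with an experience of sexual assault that occurred over 12 months ago", without distress, although its primary objective does refer to women with sexual distress.
- **Screen.** Section 2.2 says "These questions will confirm if participants are experiencing difficulties with sex". It goes on to time since assault, current psychological treatment and access to a device. The PHQ-2 and GAD-2 are included for description only. A risk item and a support question complete the list.
- **Screening call.** Its purpose is "to verify risk, confirm consent and answer any additional questions about the study".
- **FSDS-R.** After the call, section 2.2 continues: "In addition, participants will complete the Female Sexual Distress scale". Sections 2.1 and 3 likewise give it to women already found eligible. Section 2.3.3 says "The FSDS-R is completed upon recruitment and at the 1 month follow up" and attaches no threshold.
- **Use of the measure.** The secondary objectives state "Effectiveness is measured by reduction in the measure of sexual distress", together with improved sexual satisfaction. Section 3.3 says "a reliable change index (RCI) will be calculated for each measure".

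**The concern.** The criterion concerns distress and the screening question concerns difficulties. The study treats function and distress as separate enough to measure with two instruments, the FSFI and the FSDS-R. The Session 1 handout in the intervention manual lists lower sex drive, higher sex drive and less frequent sex among common experiences after sexual trauma. A woman may report any of these without being distressed by it.

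If such a woman enrols, two outcomes are affected. Her FSDS-R may start too close to 0 for any fall to count as reliable, so her RCI says nothing about the intervention. She may also have little basis for answering the VAS items that ask how she reacts when sexually distressed. With a minimum of 6 participants, a few such women could make the effectiveness results hard to read.

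**Working it through.** **Step 1: does any described step test the criterion?**

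| Step | What it covers | Tests distress? |
|---|---|---|
| Screening questions (2.2) | Difficulties with sex, time since assault, current treatment, device access, PHQ-2 and GAD-2, risk, support | Not as described |
| Screening call (2.2) | Risk, consent, questions | Not as described |
| Exclusion criteria (2.2.2) | Acute mental health, recent assault, suicidality and self-harm | No mention of low distress |
| FSDS-R (2.1, 2.2, 2.3.3, 3) | Completed after eligibility, no cut-off | Measures it, but does not decide entry |

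**Step 2: the floor on the FSDS-R.** The plan states no figure here, so there is none to reproduce.

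Inputs from the documents: 13 items scored 0 to 3 (section 2.3.3), so the range is 0 to 13 × 3 = 39. Section 3.3 names the Jacobson-Truax RCI.

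Inputs assumed, because the documents do not give them: SD 8 to 12, reliability r 0.85 to 0.95, critical value 1.96 (two-sided 5%).

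Smallest reliable drop = 1.96 × SD × √(2 × (1 − r)).

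- Low end: 1.96 × 8 × √(2 × 0.05) = 4.96.
- High end: 1.96 × 12 × √(2 × 0.15) = 12.88.

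| Assumed SD | r = 0.85 | r = 0.90 | r = 0.95 |
|---|---|---|---|
| 8 | 8.6 | 7.0 | 5.0 |
| 10 | 10.7 | 8.8 | 6.2 |
| 12 | 12.9 | 10.5 | 7.4 |

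The largest possible fall equals the baseline score. A woman whose baseline is below the value in the table cannot show a reliable reduction even if she reaches 0. In whole scores, that means baselines of 0 to 4 at the low end and 0 to 12 at the high end. Wider assumptions (SD 6 to 12, r 0.70 to 0.95) give 3.7 to 18.2 points.

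Per item, 12.88 / 13 = 0.99 and 4.96 / 13 = 0.38. Within the main range, the women affected are those whose average answer falls below 1, the option labelled rarely.

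**Step 3: the VAS.** Of the six items in section 2.3.2, four (shame, guilt, self-criticism, compassion) are conditional on the woman experiencing sexual distress. Normalising and motivation are not.

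**The case against.** Several points on the other side are sound.

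- **The form itself is not in the documents.** Section 2.2 summarises the screening questionnaire. A reader might infer that it contains no distress item, but the text supports only the statement that none is described. The criterion in 2.2.1 applies in either case.
- **The documents use the two words loosely.** The background and the compassion VAS item move between difficulties and distress as if they were close in meaning. The handout list also includes fear of sex, painful sex, shame and flashbacks, which are likely to carry distress. So the authors may have meant distress. That is a reason to say it in the question.
- **Very low distress may be uncommon.** Recruitment runs through a sexual wellbeing service, a survivors' organisation, and social media via charities and communities working with survivors. Nothing in the documents gives a frequency.
- **The FSDS-R is collected on recruitment.** It would be wrong to say that it is absent at entry. It has no part in deciding eligibility.

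Two stronger readings are tempting. One is that each low scorer becomes an automatic failure and removes a sixth (17 percentage points) from the best attainable result in a sample of 6. Section 3.3 defines no proportion reliably improved and does not say how such a woman would be reported, so the documents give no statistic to which that loss applies. The other is that low scorers should be left out of the denominator. With no control group, counting only higher baseline scorers favours apparent improvement through regression to the mean, and the cut-off would rest on RCI inputs that the plan has not fixed.

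**Conclusion.** The gap holds in a limited form. As described, no step before enrolment tests the distress criterion in 2.2.1, so a woman with difficulties but little distress could be admitted. If her baseline FSDS-R lies below the smallest reliable drop, a reliable reduction is arithmetically impossible for her. That drop is about 5 to 13 points out of 39, and it rests on the assumed SD, reliability and critical value above.

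The calculation shows that the problem is possible, not that it would be common. The consequences are bounded: feasibility and acceptability are primary, effectiveness is an initial indicator, and other measures are also analysed. A floor works against a claim of benefit, not for one. This is a cheap improvement to the plan, and the study does not fail without it.

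**What to change.** 1. **Section 2.2.** Reword the screening question to ask whether the woman is distressed or bothered by her difficulties with sex, so that it tests what 2.2.1 requires.
2. **Section 3.3.** State the SD, reliability and critical value for the FSDS-R RCI before any data are seen. Show each woman's baseline score beside the resulting threshold and flag those for whom reliable improvement is arithmetically impossible. Keep all women in every count.

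The second change is needed as well because a yes to the reworded question does not guarantee a baseline above the threshold. The flag lets a reader distinguish a woman who did not improve from one who could not have been shown to.

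The cost is one reworded question, three prespecified values, and a reporting line that uses scores already collected. The downside is slightly fewer eligible women.
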